15.2.4 Sensitivity Analysis of Secondary Effectiveness Variables

The same models as in the secondary analysis will be fitted for PPS, and corresponding descriptive statistics will be also presented.

15.3 Exploratory Effectiveness

If possible, subgroup analysis will be performed on the primary endpoint and all secondary endpoints at 6 and/or 12 weeks to assess the homogeneity of the treatment effect across various subgroups including history of statin administration, age, sex, and status of a dose up-titration.

The subgroups are defined in section 8.5.

The same models as in the primary and secondary analysis will be fitted for each subgroup in FAS and PPS, and corresponding descriptive statistics will be also presented.

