For patients whose LDL-C value has reached the target (LDL-C < 55 mg/dL) according to the lipid indicator test at Visit 3, they will continue treatment with the same dose for 6 weeks. If the LDL-C level has not reached target, the dose of atorvastatin should be increased to ezetimibe/atorvastatin 10/80 mg or atorvastatin 80 mg according to the group assigned. In principle, a morning visit is recommended so that the laboratory test results can be checked, and the IMP can be prescribed and taken on the same day. However, if the test results are not confirmed on the same day and a patient has enough IMP to take until the next visit, IMP compliance is checked, and the same dose of IMP (ezetimibe/atorvastatin 10/40 mg or atorvastatin 40 mg) is continued. An additional visit is made within 1 week to return the remaining IMP and receive new IMP. If the test results are not confirmed on the same day and a patient does not have remaining IMP, the investigator prescribes the same dose of IMP (ezetimibe/atorvastatin 10/40 mg or atorvastatin 40 mg) that the patient was taking previously, and an additional visit is made within 1 week to receive new IMP. Visit 4 is the end of study visit, and tests for effectiveness and safety are conducted.

Document: Document path and title

Template No.: CCI

Reference: CCI

Effective Date: 15Oct2021

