8.2 Statistical Tests and Confidence Intervals

For continuous efficacy variables (except triglycerides), the statistical comparisons between treatment groups are performed using an analysis of covariance (ANCOVA) with treatment group and history of statin administration as factors and the corresponding baseline as a covariate. For categorical efficacy variables, the statistical significance of the differences between treatment groups is tested using Chi-square test or Fisher's exact test. All the statistical tests use a two-sided test at the significance level of 0.05.

Due to the known distribution of triglycerides, normality assumption is usually difficult to satisfy. A nonparametric approach will be used for the analysis of percent change from baseline for triglycerides. The Hodges-Lehmann method will be used to estimate the median difference and its corresponding 95% CI for percent changes between the treatment groups.

Inferential conclusion will be drawn only for primary endpoint based on p-value at 0.05 significance level as described in section 15.1.2 of this analysis plan.

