8.5 Examination of Subgroups

Subgroup analyses will be conducted as stated in the exploratory analysis section 15.3.

The following subgroups will be assessed and described within the exploratory analysis sections:

- Sex: Female, Male
- Age (years): <65, ≥65
- History of statin administration: Yes, No (refer to section 8.3 for categorization)
- Status of a dose up-titration at Week 6: Yes, No
 - Yes (if study treatment dose is increased at Visit 3)
 - No (if study treatment dose is unchanged at Visit 3)

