Table 114. Proportion of patients achieving LDL-C goal of <55 mg/dL at Week 6 and 12 (without Statin Administration History in FAS)

Repeated style; see Table 20.

Table 115. Proportion of patients achieving LDL-C goal of <55 mg/dL at Week 6 and 12 (without Statin Administration History in PPS)

Repeated style; see Table 20.

Table 116. Proportion of patients achieving LDL-C goal of <70 mg/dL at Week 6 and 12 (without Statin Administration History in FAS)

Repeated style; see Table 20.

Table 117. Proportion of patients achieving LDL-C goal of <70 mg/dL at Week 6 and 12 (without Statin Administration History in PPS)

Repeated style; see Table 20.

Document: Document path and title

Template No.: CCI [REDACTED]

Reference: CCI [REDACTED]

Effective Date: 15Oct2021

Table 118. Percentage Change in LDL-C from Baseline to Week 6 and 12 (with Dose Up-Titration at Week 6 in FAS)

Repeated style; see Table 26.

Table 119. Percentage Change in LDL-C from Baseline to Week 6 and 12 (with Dose Up-Titration at Week 6 in PPS)

Repeated style; see Table 26.

Table 120. Percentage Change in HDL-C from Baseline to Week 6 and 12 (with Dose Up-Titration at Week 6 in FAS)

Repeated style; see Table 26.

Table 121. Percentage Change in HDL-C from Baseline to Week 6 and 12 (with Dose Up-Titration at Week 6 in PPS)

Repeated style; see Table 26.

Table 122. Percentage Change in non-HDL-C from Baseline to Week 6 and 12 (with Dose Up-Titration at Week 6 in FAS)

Repeated style; see Table 26.

Table 123. Percentage Change in non-HDL-C from Baseline to Week 6 and 12 (with Dose Up-Titration at Week 6 in PPS)

Repeated style; see Table 26.

Table 124. Percentage Change in Triglycerides from Baseline to Week 6 and 12 (with Dose Up-Titration at Week 6 in FAS)

Repeated style; see Table 30.

Table 125. Percentage Change in Triglycerides from Baseline to Week 6 and 12 (with Dose Up-Titration at Week 6 in PPS)

Repeated style; see Table 30.

Table 126. Percentage Change in Total Cholesterol from Baseline to Week 6 and 12 (with Dose Up-Titration at Week 6 in FAS)

Repeated style; see Table 26.

Document: Document path and title

Template No.: CCI [REDACTED]

Reference: CCI [REDACTED]

Effective Date: 15Oct2021

Table 127. Percentage Change in Total Cholesterol from Baseline to Week 6 and 12 (with Dose Up-Titration at Week 6 in PPS)

Repeated style; see Table 26.

Table 128. Proportion of patients achieving LDL-C goal of <55 mg/dL at Week 12 (with Dose Up-Titration at Week 6 in FAS)

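### Up-titration status is largely set by the Week 6 LDL-C result, so between-arm comparisons within it (exploratory Tables 118-145) are not randomised and cannot test homogeneity of effect

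*SAP*

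**What the plan says.** SAP 15.3 (and Protocol 9.3.4 in near-identical terms) sets the purpose of the subgroup analyses: "to assess the homogeneity of the treatment effect across various subgroups including history of statin administration, age, sex, and status of a dose up-titration". The method follows in SAP 15.3: "The same models as in the primary and secondary analysis will be fitted for each subgroup in FAS and PPS".

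SAP 8.5 defines the titration subgroup by what happened to the dose: "Yes (if study treatment dose is increased at Visit 3" and "No (if study treatment dose is unchanged at Visit 3". The rule behind the dose change is in SAP 4.1: "If the LDL-C level has not reached target, the dose of atorvastatin should be increased", the target being LDL-C below 55 mg/dL at Visit 3. SAP 15.1.1 makes the Visit 3 LDL-C value the Week 6 value of the primary endpoint.

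SAP 4.1 also provides for laboratory results that arrive late. The patient stays on the same dose after Visit 3, and then: "An additional visit is made within 1 week to return the remaining IMP and receive new IMP".

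The outputs are Tables 118-131 (up-titrated) and 132-145 (not up-titrated), for example "Table 118. Percentage Change in LDL-C from Baseline to Week 6 and 12 (with Dose Up-Titration at Week 6 in FAS". SAP 8.2 limits their standing: "Inferential conclusion will be drawn only for primary endpoint based on p-value at 0.05 significance level".

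**The concern.** A subgroup analysis assesses homogeneity only if the two arms are comparable within each subgroup. Randomisation secures that for sex, age and statin history. It does not for a variable measured after treatment started and affected by treatment. Up-titration status is nearly a cut-off on Week 6 LDL-C, so the Week 6 tables condition on the outcome itself and the Week 12 tables condition on an intermediate response.

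In clinical terms, a patient who gets below 55 mg/dL on atorvastatin alone is, on average, a stronger responder or started lower than one who gets there on the combination. Comparing the two does not isolate the effect of ezetimibe. Neither document notes that this factor differs in kind from the other three.

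What is at stake is interpretation. The tables would print between-arm differences with 95% CIs and, except for triglycerides, p-values. A reader could take them as evidence that the combination works less well, or unevenly, when the true effect is the same in everyone.

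**Working it through.** **Inputs from the documents.** Expected difference -10 points and SD 19 (Protocol 9.5); baseline LDL-C at least 70 mg/dL (Protocol 5.1); titration cut-off 55 mg/dL; ANCOVA on treatment, statin history and baseline (SAP 15.1.2). The planning figures reproduce: SD = (10/2.627)/√(2/50) = 19.03, and n = 2 × (1.96 + 0.842)² × 19²/10² = 56.69, about 57 per arm.

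**Hand calculation for one type of patient.** Assume baseline 100 mg/dL, a control mean change of -30% and hence an Eze/Ato mean of -40%, with normal residuals and SD 19. The 55 mg/dL cut-off is then a change of 55/100 - 1 = -45%.

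- Control: z = (-45 + 30)/19 = -0.789, density φ = 0.2921, Φ = 0.2149.
- Eze/Ato: z = (-45 + 40)/19 = -0.263, φ = 0.3854, Φ = 0.3962.
- Not up-titrated, mean = μ - 19φ/Φ: control -30 - 19 × 0.2921/0.2149 = -55.83; Eze/Ato -40 - 19 × 0.3854/0.3962 = -58.48. Difference **-2.65**.
- Up-titrated, mean = μ + 19φ/(1 - Φ): control -30 + 19 × 0.2921/0.7851 = -22.93; Eze/Ato -40 + 19 × 0.3854/0.6038 = -27.87. Difference **-4.94**.

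The true difference is -10 for every such patient, and neither stratum shows it.

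**Simulation over a range of patients.** There were 1,000,000 patients in each of 20 scenarios. Assumptions, none of them in the documents:

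- 35% of patients in statin stratum (b).
- Baseline LDL-C for strata (a)/(b), truncated at 70: N(90,20)/N(120,30), N(95,20)/N(95,20), N(100,25)/N(100,25) or N(100,25)/N(130,30).
- Control mean change for (a)/(b): -10/-10, -20/-20, -30/-30, -10/-40 or -20/-45.
- Week 12 residuals correlated 0.3, 0.6 or 0.8 with Week 6. An added titration effect equal in both arms cancels within a stratum.

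| LDL-C % change, true effect -10 | Up-titrated | Not up-titrated |
|---|---|---|
| Week 6 | -5.1 to -8.4 | -2.0 to -4.3 |
| Week 12 | -6.1 to -9.5 | -3.7 to -8.3 |

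The whole-sample ANCOVA returns -10. A simpler model without statin history, with other baselines (mean/SD from 85/12 to 130/30) and arm means of -20/-10 or -40/-30, gives Week 6 values of -4.2 to -9.0 and -1.8 to -3.9. With means of -20/-10 and 57 per arm, only about 3-12 Eze/Ato and 1-6 Ato patients are not up-titrated, so those tables would also be sparse.

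**Late results.** Suppose a random share of patients at or above 55 mg/dL, equal in both arms, is counted as No because the dose had not changed at Visit 3. The Week 6 estimate in the No stratum becomes -4.5 to -10.5 (2% of them), -5.8 to -12.8 (5%) or -7.3 to -13.4 (10%). The up-titrated estimate does not move.

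**Other lipids.** The bias depends on the residual correlation with LDL-C, which the documents do not give. For an assumed true effect of -8 with SD 17, a correlation of 0.9 gives -4.1 to -6.7 (up-titrated) and -1.5 to -3.4 (not); a correlation of 0 gives no bias.

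**Tables affected.** There are 16 ANCOVA tables (118-123, 126-127, 132-137, 140-141), 4 Hodges-Lehmann tables (124-125, 138-139) and 8 Chi-square/Fisher tables (128-131, 142-145), 28 in all.

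**The case against.** The strongest reply is that nothing depends on these tables. They are exploratory and conditional on feasibility, SAP 8.2 draws inference from the primary endpoint only, and a footnote might prevent misreading. That is a fair limit on severity. It does not answer the point, because those provisions control error rates and claims, whereas the problem here is bias against the stated purpose.

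The shells also show some awareness of the dependence. Week 6 is dropped from the <55 mg/dL tables (128-129, 142-143) and from the <70 mg/dL tables without up-titration (144-145). This stands, but those six tables still compare arms at Week 12 within a post-randomisation stratum, and Week 6 percentage change in LDL-C remains in Tables 118-119 and 132-133.

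Material bias has been quantified for LDL-C and, under an assumed correlation, for lipids that track it closely. For HDL-C and triglycerides the size is unknown, and no figure is given for the goal-attainment tables. This is correct; what holds for all 28 tables is the loss of randomised comparison.

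On late results, the additional visit falls by about Day 43 + 7 + 7 = 57, inside the Week 6 window of Days 14-64, so counting such patients as Yes is a possible reading. But that window assigns assessments, not dose changes, and SAP 8.5 says at Visit 3. At 5% misclassification the No estimate went beyond -10 in only 4 of 20 scenarios, all with a control change of -10/-10. The direction of bias in that stratum is therefore unfixed only under some assumptions.

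**Conclusion.** The concern holds. Up-titration status is a post-randomisation variable close to a threshold on the primary outcome measurement, and between-arm models within it cannot show whether the treatment effect is homogeneous. Confidence in that is high, because it follows from the titration rule and the subgroup definition alone.

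The size is less certain. Under the scenarios used, a uniform -10 points loses roughly 1.6 to 4.9 points at Week 6 in the up-titrated stratum (10 - 8.4 and 10 - 5.1) and 5.7 to 8.0 in the other (10 - 4.3 and 10 - 2.0). These figures rest on assumed baselines, control responses, stratum share and correlations. Bias is also expected for non-HDL-C and total cholesterol. The change should be made, but it is not critical: the primary analysis, alpha and sample size stand as they are.

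**What to change.** 1. Remove up-titration status from the homogeneity subgroups in SAP 15.3 and 8.5, and align Protocol 9.3.4.
2. Present Tables 118-145 as within-arm descriptive summaries, with no between-arm difference, CI or p-value.
3. State in SAP 8.5 how a patient whose dose changed at the additional visit is classified.
4. A separable, smaller point: for sex, age and statin history, keep the per-subgroup estimates and, for the ANCOVA endpoints, add a treatment-by-subgroup interaction estimate with 95% CI from a single model. Separate models do not directly estimate heterogeneity.

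The cost is modest. Most of the 28 tables borrow the shells of Tables 20, 26, 30 or 128, and the first three also serve other analyses, so descriptive shells must be written; rows cannot simply be deleted from the shared ones. SAP section 2 says the SAP supersedes the protocol's statistical sections, so the change can be carried there without waiting for a protocol amendment. It should be recorded in SAP 4.5, which currently lists no change from the protocol. No new data are needed and the primary analysis does not change.

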4. STUDY DESIGN

4.1 General Description

This is a phase 4, multicenter, randomized, open-label, active-controlled study. The study has been designed to evaluate the effectiveness and safety of early add-on of ezetimibe with atorvastatin in very high-risk patients.

In Visit 1, screening is conducted for patients in the very high-risk group. LDL-C needs to be above 70 mg/dL in patients (a) who failed to achieve their target LDL-C goals with mild to moderate intensity statin; (b) who are statin-naïve or have not been on a stable statin regimen for at least 4 weeks prior to enrollment. However, by tracking the registration status of patients, (b) patients should be enrolled not to exceed 40% of each group. All laboratory tests are performed in the local laboratory and the Visit 1 results may be substituted if available within 2 weeks prior to the screening visit. The study participation is determined through the inclusion/exclusion criteria based on the test results conducted for Visit 1. In the case of the lipid parameter, Visit 1 results are used as the baseline. Individuals who do not meet the criteria for participation in this study (screen failure) may be rescreened once.

In Visit 2, randomization is performed on patients who meet the inclusion criteria and do not meet any of the exclusion criteria and will be distributed 1:1 between test group (arm Eze/Ato) and control group (arm Ato). The results of laboratory tests at the Visit 2 are used as baseline except lipid parameters. Visit 1 and Visit 2 may be conducted on the same date.

In Visit 2 and Visit 3, the appropriate investigational medical product (IMP) is given to each group. In principle, IMPs are administered orally once a day from the day of distribution.

Document: Document path and title

Template No.: CCI

Reference: CCI

Effective Date: 15Oct2021

[figure not shown]

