4.2 Sample Size

The number of patients in each treatment group is about 57, assuming that the treatment difference in percentage change in LDL-C between Ezetimibe/Atorvastatin and Atorvastatin would be 10% with an SD of 19%. This calculation is based on a two-sided significance level $\alpha = 0.05$, power $1-\beta = 0.80$ with a randomization ratio $\lambda = 1$. Considering the dropout rate of 10%, 63 patients for each group and thus, a total of 126 patients will be randomized in this study.

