15.1.2 Primary Analysis of Primary Effectiveness Variable

The primary endpoint analysis will be performed on the FAS.

The statistical hypothesis of this study is as follows.

$$H_0: \mu_t - \mu_c = 0 \text{ vs. } H_1: \mu_t - \mu_c \neq 0$$

Document: Document path and title

Template No.: CCI

Reference: CCI

Effective Date: 15Oct2021

μ_t = Percentage change in LDL-C from baseline to 6 weeks in ezetimibe/atorvastatin 10/40 mg
 μ_c = Percentage change in LDL-C from baseline to 6 weeks in atorvastatin 40 mg

The primary endpoint will be analyzed by fitting an ANCOVA model with treatment group (Eze/Ato, Ato) and history of statin administration (Yes, No) as fixed effects and baseline LDL-C as a covariate. In addition to descriptive statistics for LDL-C at each visit and its percentage change from baseline by treatment group, least squares (LS) means for each treatment group with corresponding standard errors (SEs) and treatment differences of LS means with corresponding two-sided 95% confidence interval (CI) and p-value which will be derived from the fitted model will be presented. If the upper limit of the 95% two-sided CI for the corresponding treatment difference (Eze/Ato - Ato) is less than 0, Eze/Ato is considered superior to Ato.

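### The subgroup plan aims to assess homogeneity of the treatment effect, but no planned output estimates or tests a difference between subgroups

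*SAP*

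**What the plan says.** SAP 15.3 plans subgroup analyses, where feasible, of the primary and all secondary endpoints "to assess the homogeneity of the treatment effect across various subgroups including history of statin administration, age, sex, and status of a dose up-titration". Protocol 9.3.4 gives the same aim and no method.

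The SAP's method is one sentence in 15.3: "The same models as in the primary and secondary analysis will be fitted for each subgroup in FAS and PPS". For LDL-C that is the model of SAP 15.1.2, an "ANCOVA model with treatment group (Eze/Ato, Ato) and history of statin administration (Yes, No) as fixed effects and baseline LDL-C as a covariate". SAP 8.3 and 15.2.3 use the same three terms. None of these sections has a treatment-by-subgroup term.

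The shells for the baseline subgroups (sex, age group, statin history) are Tables 34 to 117. They reuse the layouts of Tables 20, 26 and 30, and none has a row for an interaction or a between-subgroup contrast. The Table 20 and Table 26 layouts carry a treatment p-value; the triglyceride layout (Table 30) does not.

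SAP 8.2 sets the general level, "All the statistical tests use a two-sided test at the significance level of 0.05", and then reserves inferential conclusions for the primary endpoint as tested under 15.1.2.

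**The concern.** Homogeneity is a question about the difference between two treatment effects. Separate models answer another question: whether the effect differs from zero in each level on its own. Each p-value depends on the size of its level as well as on the effect there, so one small and one large p-value say little about whether the effects differ.

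Two things are at stake. The stated aim gets no estimate and no interval. In addition, the tables set many within-subgroup p-values side by side, and the habitual reading (significant here, not significant there) can suggest a difference that is not real.

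**Working it through.** **Inputs.** SAP 4.2: "The number of patients in each treatment group is about 57"; planned difference 10 points, SD 19; two-sided 0.05; 1:1 allocation. SAP 4.1 caps statin stratum (b) at 40% of each group, so 60/40 is the most even statin-history split allowed. The documents give no age or sex split; 50/50 to 80/20 is my assumption.

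**The plan's own figure.** n = 2 × (1.96 + 0.842)² × 19² / 10² = 56.69, that is 57 per arm, as in Protocol 9.5. Power at 57 per arm is 80.2% by the normal approximation and 79.5% by the noncentral t.

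**Illustration: uniform effect, separate tests.** Let the true difference be 10 and the SD 19 in both levels. For a level with n per arm, power is P(|T| > t(0.975, 2n − 2)), where T is noncentral t with noncentrality (10/19) × √(n/2). The two levels contain different patients, so the tests are independent and

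P(exactly one significant) = p1(1 − p2) + p2(1 − p1).

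| Split | n per arm in each level | p1, p2 | Exactly one significant |
|---|---|---|---|
| 50/50 (assumed) | 28, 29 | 0.490, 0.504 | 0.490×0.496 + 0.504×0.510 = 50% |
| 60/40 (statin-history cap) | 34, 23 | 0.571, 0.415 | 0.571×0.585 + 0.415×0.429 = 51% |
| 75/25 (assumed) | 43, 14 | 0.675, 0.269 | 0.675×0.731 + 0.269×0.325 = 58% |
| 80/20 (assumed) | 46, 11 | 0.704, 0.217 | 0.704×0.783 + 0.217×0.296 = 62% |

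With all 63 randomized per arm evaluable, the first three rows become 50%, 51% and 59%.

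**Sensitivity to the true effect** (SD 19, splits 50/50, 60/40, 75/25): a difference of 5 gives 27.5%, 27.6%, 28.3%; 15 gives 28%, 31%, 48%; 20 gives 5%, 7%, 24%. For a difference of 10 with SD 15 to 22, the normal approximation gives 41% to 58%.

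**What an interaction analysis offers.** SE of the difference between two subgroup effects = 19 × √(2/n1 + 2/n2). The difference detectable with 80% power is 2.802 × SE.

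| Split | SE (points) | Detectable difference | Power for a 10-point difference |
|---|---|---|---|
| 50/50 | 7.1 | 20 | 29% |
| 60/40 | 7.3 | 20 | 28% |
| 75/25 | 8.3 | 23 | 23% |
| 80/20 | 9.0 | 25 | 20% |

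Under a uniform effect an interaction test at 0.05 flags a difference in about 5% of trials per factor (4.9% to 5.2% in 4,000 simulated trials). Over three independent factors that is 1 − 0.95³ = 14% for at least one flag.

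**Number of p-values.** Tables 34 to 117 are 84 shells (6 levels × 7 endpoints × 2 analysis sets). Twelve are triglyceride tables. The other 72 show p-values at weeks 6 and 12, which makes 144.

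**A side effect of the literal plan.** Within each statin-history subgroup the statin-history factor is constant, so the same model cannot be fitted there as written.

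**The case against.** The strongest defence is that the plan already limits the damage. SAP 15.3 sits under exploratory effectiveness, and SAP 8.2 draws inferential conclusions from the primary endpoint only, so claiming that the combination works in some patients and not in others would contradict the SAP. This stands, and it lowers the consequence.

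A reader might infer that the trial would call a uniform effect uneven about half the time. The documents do not support that. No section makes significance in one level and not the other a decision rule, and the shells also show estimates and intervals that can be compared informally. The 50% describes a misreading that the tables invite. It applies to week-6 LDL-C near the planned effect and partly rests on assumed splits. The SD of 19 was also derived from an unadjusted t statistic, and the residual SD after covariate adjustment may differ.

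A reader might also infer that every subgroup table carries a p-value. The triglyceride tables follow the Table 30 layout, which has none. The exception is Table 111, which points to Table 26 and so conflicts with the nonparametric method of SAP 15.2.3.

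Finally, an interaction test has little power here. That is true, and it is a reason to report the interaction with its interval. Separate models rest on the same limited information but do not show how imprecise the comparison is. The defence does not supply the missing comparison.

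**Conclusion.** The point holds as a gap between aim and method: homogeneity is the declared purpose in both documents, and no planned output estimates or tests it for the baseline subgroups. It is worth correcting, but it does not threaten the primary conclusion.

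Its size as a risk of misreading is about 50% to 62% of trials with exactly one level significant under a uniform effect. This assumes a true difference of 10, SD 19, 57 per arm and splits from 50/50 to 80/20. For splits of 50/50 to 75/25 it falls to about 27–28% at a true difference of 5 and to 5–24% at 20. It would also be too strong to say that an interaction test settles the matter: at this sample size it can exclude only large differences.

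**What to change.** In SAP 15.3, for sex, age group and statin history:

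- **LDL-C and the other ANCOVA-analysed lipids.** Fit one ANCOVA on the whole FAS, repeated in the PPS, with treatment, baseline value, statin history, subgroup and treatment-by-subgroup. For the statin-history subgroup, enter statin history once plus its interaction with treatment; this also removes the constant-factor problem.
- **Reporting.** Give the interaction estimate with its 95% CI and nominal p-value. Take the subgroup-specific differences and CIs from that model. Drop the within-subgroup treatment p-values from Tables 34 to 117 and add an interaction row.
- **Goal attainment.** Report the difference between the two subgroup risk differences with its 95% CI.
- **Triglycerides.** Keep the subgroup Hodges-Lehmann estimates and CIs as descriptive, and point Table 111 to Table 30.
- **Caveats to state.** The interaction SE for week-6 LDL-C is about 7 points or more; about a 20-point difference (more with uneven splits) is detectable with 80% power; a non-significant interaction does not establish homogeneity; the tests are exploratory and unadjusted for multiplicity.

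Up-titration status (Tables 118 to 145) is set by the Visit 3 LDL-C result, after randomization. It is a separate matter and not part of this change.

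The cost is SAP wording, revised shells and modest programming. Conduct, sample size and the primary analysis do not change. The intervals will be wide, and the report has to say so.
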